### 5.2.2 Data Collected for Withdrawn Subjects

Patients may withdraw from the study or discontinue study treatment at any time; however, CytoDyn is dedicated to minimizing missing data in this study. It is therefore suggested that all patients, regardless of whether they continue to receive study treatment, continue within the study.

Investigators considering discontinuing study treatment should contact the medical monitor prior to such discontinuation. Patients who have study treatment discontinued will continue to be followed, per protocol, whenever possible. Patients who have study treatment discontinued due to a serious adverse event will be followed until resolution or stabilization of the event.

In the event that a subject is withdrawn from the study at any time due to an adverse event or serious adverse event (SAE), the procedures stated in [Section 9.1.1](#) or [9.2.1](#), respectively must be followed.

Every attempt should be made to collect follow-up information. The reason for withdrawal from the study will be recorded in the source documents and on the appropriate page of the eCRF.

Before a subject is identified as lost-to-follow up, the site should make all reasonable efforts to contact the subject. These attempts must be documented and should include at a minimum one phone call and one certified letter.

### **5.3 SCREEN FAILURES**

A subject who has signed a consent form, has been assigned a screening number, but is not treated is classified as a screen failure. Subject number, demographics and reason for screen failure will be recorded.

If a subject initially fails to meet inclusion/exclusion criteria and is later reconsidered for participation, the subject will be re-consented and assigned a new screening number at the time of re-screening. Subjects who fail their first screening attempt may be re-screened again (i.e., up to two screenings) and may be enrolled if they are found to meet all inclusion and no exclusion criteria at the subsequent screening visit.

## 6 STUDY TREATMENT

### 6.1 INVESTIGATIONAL PRODUCT DESCRIPTION

PRO 140 is a humanized IgG4, $\kappa$  monoclonal antibody (mAb) to the chemokine receptor CCR5. PRO 140 is provided at a concentration of 175 mg/mL and is intended for SC route of administration.

Kits will be labeled with a unique identification number. Each kit used during the Treatment Phase will contain vials of PRO 140 for SC injection. One milliliter (1 mL), 1.5 mL, or 2 mL of PRO 140 solution will be drawn from a vial and loaded into the syringe. A total of 350 mg or 525 mg or 700 mg (175 mg/mL) of PRO 140 is delivered as two injections administered subcutaneously on opposite sides of the abdomen or as one of the alternative methods listed in Section 6.4 below. One study injection kit will be assigned per subject per treatment visit (with exception for 350 mg dose with 2.4 mL fill volume in which one kit can be used for two doses).

PRO 140 Kits Containing 1.4 mL per Vial				
PRO 140 Dose	# of Vials Used per Dose	Total Injection Volume (mL)	Volume (mL) Administered per Injection*	Volume (mL) Discarded per Vial
350 mg	2	2	1	0.4
525 mg	3	3	1.5	0.4
700 mg	4	4	2	0.4
PRO 140 Kits Containing 2.4 mL per Vial				
PRO 140 Dose	# of Vials Used per Dose	Total Injection Volume (mL)	Volume (mL) Administered per Injection*	Volume (mL) Discarded per Vial
350 mg	1**	2	1	0.4
525 mg	2	3	1.5	0.9
700 mg	2	4	2	0.4

\*When 2 injections given per dose; 1 injection on opposite sides of the abdomen.

\*\*Since each vial contains 2.4 mL of PRO 140, only 1 vial is needed for the 350 mg dose. The second vial can be utilized to administer 350 mg dose at the subsequent visit.

Each vial of the PRO 140 product contains ~1.4 or 2.4 mL antibody at 175mg/mL in a buffer containing 5 mM L-histidine, 15.0 mM glycine, 95 mM sodium chloride, 0.3% (w/v) sorbitol, 0.005% (w/v) polysorbate 20 (Tween 20®), and sterile water for injection, at pH of 5.5.

**Note:** 1 mL injection will be drawn from 1.4 mL solution in a vial. Remaining 0.4 mL medication will be discarded appropriately from each vial.

Subjects in Group B may require three vials and subjects in Group C may require four vials for single dose. Unused content of PRO 140 in a vial should remain in the vial and **not** be administered to any other subject.

Alternatively, when 2.4 mL vials are provided, 1.5 or 2 mL injection will be drawn and the remaining will be discarded from each vial. Subjects in both group B and C will require two vials for a single dose. Unused content of PRO 140 in a vial should remain in the vial and **not** be administered to any other subject.

Table 6-1 provides the unit strength, dosing frequency and mode of administration for the study drug.

**Table 6-1: Investigational Product - PRO 140**

IP Dosage	Dosage Form	IP concentration	Dosing Frequency and Amount	Route of Administration
PRO 140 350mg	Parenteral solution	175 mg/mL	2 injections of PRO 140 (1 mL/inj.) per week on opposite sides of abdomen for up to 48 weeks (T1 – T48)	SC injection
PRO 140 525 mg	Parenteral solution	175 mg/mL	2 injections of PRO 140 (1.5 mL/inj.) per week on opposite sides of abdomen for up to 48 weeks (T1 – T48)	SC injection
PRO 140 700 mg	Parenteral solution	175 mg/mL	2 injections of PRO 140 (2 mL/inj.) per week on opposite sides of abdomen for up to 48 weeks (T1 – T48)	SC injection

## 6.2 INVESTIGATIONAL PRODUCT PACKAGING AND LABELING

Study drug will be prepared by Ajinomoto Althea, Inc. and will be packaged, labeled, and shipped by Sherpa Clinical Packaging, LLC.

The contents of each vial are described in Section 6.1. PRO 140 kits will be labeled with information such as: study protocol #; fill volume; concentration; storage condition; a “use as per study protocol” statement; a cautionary statement; sponsor’s name and address; and the kit number.

**Figure 6-3: PRO 140 (CHO) 175mg/mL - Kit Label**

Protocol: PRO 140_CD03	Kit No. xxx
Site No. _____	Subject No. _____
This kit contains 2 single-use vials	
Each 3 mL vial contains 1.4 mL of PRO 140 (175 mg/mL) solution for subcutaneous injection	
Store at 2°C to 8°C (36°F to 46°F)	
USE AS PER STUDY PROTOCOL	
Caution: New Drug – Limited by Federal (or United States) Law to Investigational Use	
CytoDyn Inc., Vancouver, WA, USA	

Protocol: PRO 140_CD03	Kit No. xxx
Site No. _____	Subject No. _____
This kit contains 3 single-use vials	
Each 3 mL vial contains 1.4 mL of PRO 140 (175 mg/mL) solution for subcutaneous injection	
Store at 2°C to 8°C (36°F to 46°F)	
USE AS PER STUDY PROTOCOL	
Caution: New Drug – Limited by Federal (or United States) Law to Investigational Use	
CytoDyn Inc., Vancouver, WA, USA	

Protocol: PRO 140_CD03	Kit No. xxx
Site No. _____	Subject No. _____
This kit contains 4 single-use vials	
Each 3 mL vial contains 1.4 mL of PRO 140 (175 mg/mL) solution for subcutaneous injection	
Store at 2°C to 8°C (36°F to 46°F)	
USE AS PER STUDY PROTOCOL	
Caution: New Drug – Limited by Federal (or United States) Law to Investigational Use	
CytoDyn Inc., Vancouver, WA, USA	

Protocol: PRO 140\_CD03

Kit No. xxx

Site No. \_\_\_\_\_

Subject No. \_\_\_\_\_

**This kit contains 2 single-use vials**

Each 3 mL vial contains 2.4 mL of PRO 140 (175 mg/mL) solution for subcutaneous injection

Store at 2°C to 8°C (36°F to 46°F)

USE AS PER STUDY PROTOCOL

Caution: New Drug – Limited by Federal (or United States) Law to Investigational Use

Cytodyn Inc., Vancouver, WA, USA

*Note: Subjects in Group B will receive two injections of 1.5mL each of study treatment and subjects in Group C will receive two injections of 2mL each of study treatment for single dose.*

*Patients with low body fat percentages may find subcutaneous injections uncomfortable esp. in case of 1.5 mL or 2mL injection for the 525 mg or 700mg dosing, respectively. In such cases, PRO 140 525 mg can be injected as three 175mg/ml injections, or PRO 140 700 mg can be injected as four 175mg/ml injections and/or subcutaneous injections can be placed at different areas other than abdomen as per discretion of the Investigator.*

The pharmacy manual provides the criteria regarding vial acceptance or rejection, as well as instructions for the preparation of the IP syringes to be used to administer drug.

### 6.3 INVESTIGATIONAL PRODUCT STORAGE

Study drug will be shipped at 2°C to 8°C (refrigerated [36°F to 46°F]) to the Investigator's site. Upon receipt at the site, the responsible site staff or pharmacist should verify the integrity of the vials. Study drug should be stored at 2°C to 8°C (refrigerated [36°F to 46°F]). The contents of the vial should appear as a clear to opalescent, colorless to yellow solution; fine translucent particles may be present. This is normal.

The Investigator must maintain an accurate record of the shipment, storage, and dispensing of the study drug in a drug accountability log. An accurate record including the date and amount of study drug dispensed for each subject must be available for inspection at any time. A study CRA assigned to monitor the investigational site will review these documents once study drug has been received by the investigational site. Study drug will be accounted for on an ongoing basis during the study.

### 6.4 INVESTIGATIONAL PRODUCT ADMINISTRATION

Guidelines for dose preparation can be found in the pharmacy manual.

PRO 140 will be provided to the administering personnel in single-use syringes prepared from vials of study drug stored at 2-8°C at the site pharmacy prior to use. Each of two syringes is filled to deliver 1.0 mL, if receiving 350mg dose (or 1.5 mL, if receiving 525mg dose or 2 mL, if receiving 700mg dose) of study drug.

Equivalent volumes of study drug will be administered subcutaneously on opposite sides of the abdomen. However, based on subject preference or investigator discretion, subjects receiving each of the doses can be administered using an alternate approach as follows:

**350mg Dose:**

- One 2 mL injection on one side of the abdomen.

**525mg Dose:**

- One 3 mL injection on one side of the abdomen.
- Three 1 mL injections, two on one side of the abdomen and one on the other side.

**700 mg Dose:**

- Four 1 mL injections, on opposite sides of the abdomen, or other location.

A 25-gauge needle should be used to remove IP from vial and for administration to subjects, and drug should not be held in syringe for longer than 1 hour.

IP should be administered slowly over 15 seconds per mL.

Following each SC delivery of drug, careful examination will be made to assess the appearance of any study drug Injection Site Reactions (ISRs) as described in [Section 17.3](#).

All doses of study drug will be administered as SC injection by a qualified medical professional (MD, DO, PA, LPN, LVN, NP, RN or CMA if permitted by state law) at clinic site or home visit or self-administered by subjects.

## **6.5 INVESTIGATIONAL PRODUCT RECEIPT AND ACCOUNTABILITY**

Study drug must be used in accordance with this protocol and only under the direction of the responsible Investigator. The investigational site must maintain complete and accurate records showing receipt and disposition of all study drug, including master records listing the date of receipt, the number and nature of medication units received, and a dispensing record which includes each quantity dispensed, identification of the staff member/subject to whom dispensed, the date of dispensing, the intended study participant, and the identification of the preparer. All used and unused study kits will be retained by the investigational site until drug accountability can be confirmed by study CRA during the monitoring visits. Instructions will be provided by Sponsor regarding final disposition of all study drug in compliance with applicable regulations.

## **6.6 INVESTIGATIONAL PRODUCT DISPOSITION**

All drug supplies are to be used only for this protocol and not for any other purpose. The Investigator must not destroy any drug labels or any partially used or unused drug supply until instructed by the Sponsor. At the conclusion of the study and as appropriate during the course of the study, the Investigator will return all used and unused drug containers and drug labels to the drug distributor as directed by the Sponsor. A copy of the completed drug disposition form will be sent to CytoDyn, Inc. or to its designee.

## 7 DESCRIPTION OF PROTOCOL ASSESSMENTS AND PROCEDURES

### 7.1 INFORMED CONSENT

Written informed consent will be obtained for this study by the Investigator or designee from all subjects before the performance of any protocol-specific procedure. This study will be conducted in accordance with the provisions of the Declaration of Helsinki.

In obtaining and documenting informed consent, the Investigator must comply with applicable regulatory requirements and must adhere to Good Clinical Practice (GCP). The Investigator, or designee, must fully inform subjects of all pertinent aspects of the study. Before informed consent may be obtained, the Investigator, or a person designated by the Investigator, must provide the subject ample time and opportunity to inquire about details of the study and to decide whether or not to participate in the trial. All questions about the trial must be answered to the satisfaction of the subject. Prior to the subject's participation in the trial, the written informed consent must be signed and personally dated by the subject and by the person who conducted the informed consent discussion. Authorization for release of protected health information must also be obtained, as per local policies.

### 7.2 ASSESSMENT OF ELIGIBILITY

During the Screening Phase and at T1 Visit (prior to treatment administration), the Investigator must assess a subject's continued suitability and eligibility for the trial. The Inclusion and Exclusion criteria of this Protocol are described in [Sections 3.3.1](#) and [3.3.2](#). If the subject is not suitable or eligible for the trial then the subject will be a screen failure.

#### 7.2.1 Re-screening

If a subject initially fails to meet inclusion/exclusion criteria, and is later reconsidered for participation, the subject will be re-consented and assigned a new screening number at the time of re-screening. Subjects who fail their first screening attempt may be re-screened a maximum of once and may be enrolled if they are found to meet all inclusion and no exclusion criteria when re-screened.

### 7.3 DEMOGRAPHIC INFORMATION

For the purposes of this study, demographic information will include:

- Dates of ICF signature
- Date of birth
- Gender

- Race (American Indian/Alaskan Native, Asian, Black/African American, Native Hawaiian/Pacific Islander, Caucasian, or other)
- Ethnicity (Hispanic/Latino or Not Hispanic/Latino)

#### 7.4 MEDICAL HISTORY

A medical history will be recorded during the Screening Phase and will include:

- All ongoing medical conditions
- Disease history (HIV), history of substance abuse, social history, blood transfusion history and any past surgeries
- All previously resolved medical conditions related to HIV or which are relevant in the judgment of the Investigator
- Any prior medical conditions that have resolved within the last year

Events that emerge prior to the first treatment (T1) will be recorded in the medical history and not as AEs. Aside from being used to determine subject eligibility, this information will permit the Investigator to record the nature, duration and severity of any ongoing baseline medical conditions prior to the patient's receiving investigational product (IP) treatment.

Medical histories will be recorded using the body system categories outlined below:

- |                    |                 |
|--------------------|-----------------|
| • Cardiovascular   | • Lymphatic     |
| • Respiratory      | • Hematologic   |
| • Gastrointestinal | • Immunologic   |
| • Renal            | • Dermatologic  |
| • Hepatic          | • Psychiatric   |
| • Neurological     | • Genitourinary |
| • Endocrine        | • Other         |

For each relevant history, the following will be documented:

- Disease/disorder/condition
- Date of diagnosis
- History status (resolved or ongoing)

#### 7.5 PRIOR / CONCOMITANT MEDICATIONS AND NON-STUDY TREATMENTS

A complete history of antiretroviral therapies will be recorded in the source documents and on the appropriate page of the eCRF.

In addition to this, all other medications and therapies administered or taken by the subject beginning 30 days prior to first Screening Visit and throughout the study will be recorded. Subjects must be questioned at each study visit concerning any new medications or changes in current medications including over-the-counter medication.

For each medication and non-study treatment, the following will be documented:

- Medication/treatment name (generic name may be used if trade name is unknown)
- Dose, unit, and frequency of dosing (individual dosages, not total daily dose).
  - **Note:** *Each new dose of medication should be recorded as a separate entry, with the exception of medications that are given on a sliding scale. For these, it is acceptable to enter the range of the dosage, including the start and stop dates for which the specified dosage range was used.*
- Route of dosing
- Indication for use
- The start date
- The stop date (if medication/therapy is not ongoing)

Please refer to Exclusion Criteria ([Section 3.3.2](#)) for a list of prohibited treatments and/or procedures. All other medications that are appropriate for the care of the subject may be prescribed. If concomitant medications are started during the study, the indication for the concomitant medication should be considered an AE.

### 7.5.1 Excluded Medications and Therapies

1. Use of concomitant antiretroviral therapy is NOT allowed during the Treatment Phase of the study EXCEPT for one week overlap of existing retroviral regimen and PRO 140 at the beginning of the study treatment and also one week overlap at the end of the treatment in subjects who do not experience virologic failure. Subject is allowed to re-initiate antiretroviral therapy during the Treatment Phase, if virologic failure occurs or if subject meets any other criteria for discontinuation of study treatment as specified in [Section 5.2.1](#) of the protocol.
2. Use of oral or parenteral corticosteroids (> 5 mg/day) is NOT allowed during the study, with the following exceptions:
  - Use of chronic systemic corticosteroids at replacement doses (e.g., < 5mg/day prednisone) AND use of inhaled, nasal, or topical steroids are allowed.

- Use of short course of systemic corticosteroids (Medrol pack) after T2 will only be allowed with prior approval from the sponsor.
- 3. Use of radiation or cytotoxic chemotherapy, immunosuppressants and immunomodulating agents (e.g., interleukins, interferons) or agents with known anti-HIV activity (i.e., hydroxyurea, foscarnet) are NOT allowed during the study.
- 4. Use of any non-FDA approved/investigational therapy

### **7.5.2 Allowable Medications and Therapies**

All other medications/therapies that are not otherwise prohibited and, in the judgment of the Investigator, are required for proper medical care of the subject may be prescribed.

## **7.6 PHYSICAL EXAMINATION**

The complete physical examination will include routine examinations for the following:

- General Appearance
- Head, Ears, Eyes, Nose, Throat (HEENT)
- Lymph Nodes
- Heart/Cardiovascular abnormalities
- Respiratory
- Abdomen
- Genitourinary
- Musculoskeletal and Extremities
- Neurologic abnormalities
- Dermatologic abnormalities
- Any other body system for which an abnormality is noted and which, in the opinion of the Investigator, is relevant to the safety of the subject or could impact safety or efficacy results for the subject; i.e., the abnormality is clinically significant (CS).

Each abnormality will be recorded and the Investigator will record an assessment of its clinical significance.

The complete physical examination will be conducted at the Screening Visit (SV), Treatment Visit 48 (T48), and at Virologic Failure (VF) Visit. Only symptom-directed physical examination will be performed at treatment and follow-up visits conducted within the clinic, and at unscheduled visits within the Treatment and Follow-up Phases.

## 7.7 ELECTROCARDIOGRAM

A resting 12-lead ECG will be conducted at the Screening Visit (SV) and at T48 or Virologic Failure (VF) visit and the results will be evaluated by the Investigator. The following parameters will be recorded: ventricular rate (beats per minute), PR interval (msec), QRS interval (msec), QT interval (msec), and QTc interval (msec). Additionally, the Investigator will record the overall results of the ECG reading as either normal or abnormal, and as either not clinically significant or clinically significant. If abnormalities are observed, each will be recorded.

Only those subjects who have normal or not-clinically significant results at the Screening Visit (SV) will be enrolled in this study.

## 7.8 NEUROLOGICAL ASSESSMENT

Neurological assessment will be performed by the Principal Investigator or Study Coordinator at Treatment Visits 1, 16 and 48 (T1, T16, T48) and at Virologic Failure (VF) Visit.

The neurological assessment tool is based on the three question survey used by Simioni et al. (Simioni S, 2010). Refer to [Section 17.4](#) for further details. Additional neurological assessment modalities may be used as per Investigator's discretion.

## 7.9 VITAL SIGNS (INC. HEIGHT AND WEIGHT)

Vital signs will be collected at all study visits performed at the clinic. Vital signs collected during the Treatment Phase will be performed post-treatment, with the exception of pre-treatment vitals collected at T1, and assessed within 15 minutes following study treatment administration.

The following vital signs will be collected at all visits, unless otherwise stated:

- Height (at SV)
- Weight (at SV, T48 and VF visits)
- BMI (derived from the height and weight measurements; at SV, T48 and VF visits)
- Seated blood pressure (taken after the subject has been seated for at least 5 minutes)
- Heart Rate
- Respiration Rate
- Temperature

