**Foot Notes:**

- [1] Symptom-directed physical examination at clinic visits.
- [2] The neurological assessment tool is based on the three question survey used by Simioni et al. (Simioni S, 2010). Additional neurological assessment modalities may be used as per Investigator's discretion.
- [3] Post treatment vital signs (blood pressure, heart rate, respiration rate, and temperature) will be measured at clinic visit.
- [4] Hemoglobin, Hematocrit (HCT), Red Blood Cells (RBC), White Blood Cells (WBC) with total and differential count, Absolute Neutrophil Count (ANC) and platelets.
- [5] Serum Biochemistry  
 Hepatic function indicators: total and direct bilirubin, alkaline phosphatase, aspartate aminotransferase (AST), alanine aminotransferase (ALT), total protein, Lactate dehydrogenase (LDH)  
 Renal function indicators: BUN, creatinine  
 Electrolytes: sodium, potassium, chloride, calcium and bicarbonate  
 Other: glucose (random), cholesterol (total)
- [6] Blood sample for plasma HIV-1 RNA level collected at least once every four weeks between T18-21, T22-25, T26-29, T30-33, T34-37, T38-41 and T42-45 visits when subject comes to clinic.
- [7] Blood sample for TruCount T assay collected at least once every four weeks between T18-21, T22-25, T26-29, T30-33, T34-37, T38-41 and T42-45 visits when subject comes to clinic. Assay includes: Absolute Lymphocytes, CD3 cell count, CD4 cell count, CD8 cell count, CD3%, CD4% and CD8%
- [8] Monogram Biosciences GenoSure Archive Assay will be performed at T48 visit. PhenoSense® GT (and PhenoSense Integrase and GeneSeq Integrase testing, if applicable), will be performed at the time of virologic failure.
- [9] Study subjects will re-initiate their previous antiretroviral regimen or an alternative regimen selected by their treating physician: (1) One week prior to the end of 48-week Treatment Phase, or (2) Anytime during the Treatment Extension Phase, if virologic failure occurs or have met any other criteria for discontinuation of study treatment as specified in the protocol.
- [10] Injection Site Reaction Assessment as assessed by Investigator (or designee) at the clinic visits and by visiting nurse or qualified medical professional during home visits. Injection Site Reaction Assessment will not be applicable if PRO 140 is self-administered by subjects at home.

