##### Pre-Treatment

- Confirmation of eligibility criteria by reviewing test results and other criteria assessments performed at Screening Visit (see [Section 7.2](#) )
- Neurological Assessment (see [Section 7.8](#))
- Symptom-directed physical examination (see [Section 7.6](#))
- Change in concomitant medications (see [Section 7.5](#))
- Any changes in medical history since Screening Visit (see [Section 7.4](#))
- Vital Signs (see [Section 7.9](#))
  - **Note:** *Vitals will be taken twice: pre- and post-treatment. Post-Treatment Vital Signs will be assessed within 15 minutes following study treatment administration.*
- Collection of Blood Specimens (see [Section 7.10](#)) for
  - Plasma HIV-1 RNA level
  - TruCount T Assay
  - CCR5 Receptor Occupancy (IncellDx Lab)
  - HIV Drug Resistance Assay
  - PK sample for PRO 140
  - Anti-idiotypic antibodies to PRO 140
  - Blood sample for evaluation of potential biomarkers [*occurs at T1*]
    - gp120 genotypes
    - Plasma *HIV-1 RNA* Single Copy Assay
    - Immune Activation Markers
    - PhenoSense® Entry Assay [*performed at T1 using the blood sample collected for Tropism at Screening for subjects who are found eligible to be enrolled in the study*]
    - CCR5 expression levels

- Quest Diagnostics Proviral DNA® Tropism Assay [*if not performed at SV*]
- Cerebrospinal fluid (CSF) sample collection for Central Nervous System (CNS) sub-study (see [Section 7.10.16](#))
  - **Note:** CSF sample should be collected at T1 (prior to first dose of PRO 140), visit for subjects participating in CNS sub-study.
- Genital secretion sample collection for Genitourinary (GU) sub-study (see [Section 7.10.17](#))
  - **Note:** Genital secretion sample should be collected at T1 (prior to first dose of PRO 140) visit for subjects participating in GU sub-study.
- Urine Pregnancy Test (see [Section 7.10.8](#))

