### **4.2.2 Treatment Phase: Treatment Visit-2 (T2) to Treatment Visit-16 (T16)**

The following assessments will be performed at each visit, unless otherwise specified:

- Assess for any Adverse Events and changes in Concomitant medications (see [Section 9](#) and [7.5](#)),
- Symptom-directed physical examination (see [Section 7.6](#)),
- Neurological Assessment (see [Section 7.8](#)) [*occurs at T16*]
- Vital Signs (see [Section 7.9](#))
  - **Note:** *Post-treatment vital signs will be assessed within 15 minutes following study treatment administration*
- Collection of Blood Specimens (see [Section 7.10](#)) for
  - Complete Blood Count at T12 visit
  - Biochemistry at T12 visit
  - Coagulation Indices [Prothrombin time (PT) and INR] at T12 visit
  - CCR5 Receptor Occupancy (IncellDx Lab)
  - Plasma HIV-1 RNA level
  - TruCount T Assay
    - **Note:** *Blood sample for plasma HIV-1 RNA level, TruCount T Assay, and CCR5 Receptor Occupancy should be collected at T2, T4, T6, T8, T10, T12, T14 and T16 visits when subject comes to clinic.*
  - Plasma HIV-1 RNA Single Copy Assay
    - **Note:** *Blood sample for plasma HIV-1 RNA Single Copy Assay should be collected at T8 and T12 visits when subject comes to clinic.*
  - Trofile DNA Assay and PhenoSense Entry Assay at T10 visit
  - PK sample for PRO 140
  - Anti-idiotypic antibodies to PRO 140
    - **Note:** *PK and ADA blood sample should be collected at T1 (prior to first dose), T4, T8, T12 and T16 visits.*
- Collection of Urine Specimen for Urinalysis (see [Section 7.10.15](#)) at T12 visit
- Measurement of treatment adherence (see [Section 7.14](#)) at T4, T8, T12 and T16 visits
- Study Treatment Administration (PRO 140)
  - Note:** All treatment injections must be administered by a qualified medical professional

(MD, DO, PA, LPN, LVN, NP, RN or CMA if permitted by state law) at clinic site or home visit or self-administered by subjects, for the duration of 48 weeks in the Treatment Phase.

- Injection Site Reaction Assessment (see [Section 7.12](#))
  - **Note:** *To assess injection site reactions, the Investigator will use the DAIDS AE grading table (refer to [Section 17.3](#)).*
- Subject-perceived Injection Site Pain Assessment (see [Section 7.13](#))
  - **Note:** *Subject-perceived injection site pain will be assessed using the Pain Visual Analog Scale (VAS) prior to study treatment administration assessing average pain at injection site since last treatment.*

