### 8.2 DESCRIPTION OF STUDY OUTCOME MEASURES

#### 8.2.1 Primary Safety Outcome Measures

The following metrics will be analyzed to assess the clinical safety of PRO 140 monotherapy regimen:

- Incidence of Treatment-Emergent Adverse Events (TEAE)
- Incidence of Treatment-Emergent Serious Adverse Events
- Incidence of Injection Site Reactions by Investigator evaluation
- Frequency of Grade 3 or 4 adverse events as defined by the DAIDS Adverse Event scale
- Tolerability of repeated subcutaneous administration of PRO 140 as assessed by study participants (using Visual Analogue Scale)
- Changes and shifts in laboratory measurements over time
- Changes in vital signs and weight over time
- Changes and shift in Electrocardiogram (ECG) parameters over time
- Incidence of Physical Examination abnormalities over time

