7. DATA CONVENTION AND RELATED DEFINITIONS

7.1 Baseline Definition

For all parameters, baseline will be defined as the last available value prior to initiation of the first dose of PRO140.

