8.2.1.2 Vital Signs

Tabulations of raw data and change from baseline values will be presented by visit for each vital sign parameter [*i.e.*, systolic BP (mmHg), diastolic BP (mmHg), temperature ($^{\circ}$ C), heart rate (bpm), respiratory rate (rpm)].

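### Weight after screening is required by Protocol 7.9 but missing from the schedule tables, and the SAP's change in vital signs sets a pre-injection baseline against post-injection readings

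*Protocol*

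**What the plan says.** **The outcome.** Protocol 8.2.1 lists "Changes in vital signs and weight over time" among the primary safety outcome measures, and SAP 3.1.1 repeats it.

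**Weight.** Protocol 7.9 sets the time points: "Weight (at SV, T48 and VF visits", with BMI at the same three visits. Table 4-1 marks body weight and height at screening only. Table 4-2 has no weight row, and its footnote 3 defines what is taken: "Post treatment vital signs (blood pressure, heart rate, respiration rate, and temperature) will be measured at clinic visit". SAP Tables 2-1 and 2-2 carry the same rows and footnotes. SAP 8.2.4.10 says that weight is summarised and listed, and goes no further.

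**Vital signs, collection.** Protocol 7.9 states that "Vital signs collected during the Treatment Phase will be performed post-treatment, with the exception of pre-treatment vitals collected at T1". The visit text for T2 to T16 gives the window: "Post-treatment vital signs will be assessed within 15 minutes following study treatment administration". The T17 to T48 text says the same. At T1, Protocol 4.2.1 says "Vitals will be taken twice: pre- and post-treatment", with the second set in the same 15-minute window. The VF visit list (4.3) and the follow-up tables include vital signs but no PRO 140 administration.

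**Vital signs, analysis.** Under SAP 7.1, for all parameters, "baseline will be defined as the last available value prior to initiation of the first dose of PRO140". SAP 8.2.1.2 (Vital Signs) then says: "Tabulations of raw data and change from baseline values will be presented by visit for each vital sign parameter". The parameters it lists do not include weight.

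**The concern.** These are two separate problems within one outcome.

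For weight, the schedule tables and the section text disagree on whether anything is measured after screening. If a site follows the tables, change in weight has no second value for its subjects. A weight not taken at T48 or VF cannot be recovered later. Even where it is taken, the SAP does not say that a change will be reported, although change is the outcome.

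For vital signs, the data are scheduled, but the planned change column compares two measurement conditions. The trial has no untreated control and plans no inferential comparison, and the first ~150 subjects were a single arm. Within-group change is therefore what a reader of the safety tables will look at. A shift in blood pressure or heart rate could be a lasting change, a brief response to an injection given minutes earlier, or both. The change column cannot separate them.

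**Working it through.** The plan states no figure for this point, so there is none to reproduce. The check sets the passages side by side.

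**Weight time points**

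| Source | Screening | T48 | VF | Count |
|---|---|---|---|---|
| Protocol 7.9 | yes | yes | yes | 3 |
| Protocol Tables 4-1 and 4-2 | yes | no | no | 1 |
| SAP Tables 2-1 and 2-2 | yes | no | no | 1 |

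Post-screening weights: 3 − 1 = 2 time points in the text and 1 − 1 = 0 in the tables. The baseline weight under SAP 7.1 is the screening value, the only one scheduled before the first dose. A change in weight therefore exists only for subjects weighed at T48 or VF.

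**Vital signs by condition**

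| Reading | Relation to injection | Role in the SAP |
|---|---|---|
| T1, first set | before | baseline (SAP 7.1) |
| T1, second set | within 15 minutes after | none named |
| Later treatment visits at the clinic | within 15 minutes after | compared with baseline |
| VF and follow-up | no injection listed | compared with baseline |

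For one subject and one parameter, let *b*₀ be the T1 pre-injection value, *b*₁ the T1 post-injection value and *y* an on-treatment post-injection value. The planned change is

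*y* − *b*₀ = (*y* − *b*₁) + (*b*₁ − *b*₀).

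The first bracket compares post-injection with post-injection. The second is the shift across the first injection. The SAP reports only the sum. All three readings are scheduled, so both brackets can be computed without new data. For VF and follow-up readings, where no injection is listed, *b*₀ is the matching reference. The series therefore changes condition when a subject leaves weekly treatment.

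The documents give no pre- and post-injection data for any vital sign and no standard deviation. The size and sign of *b*₁ − *b*₀ cannot be computed.

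**The T2 visit.** Table 4-1 footnote 6 limits vital signs to post-treatment readings only after T2. Protocol 7.9 makes the sole exception at T1. The two differ on whether T2 also has a pre-treatment set.

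**The case against.** The case on the other side has weight.

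- **Weight is in the protocol.** The T17 to T48 and VF visit lists both call for vital signs with a cross-reference to 7.9, whose heading includes height and weight, and the vital-signs row is ticked at T48 and VF in Table 4-2. This stands. A reader might infer from the tables that no weight is collected after screening. The documents do not support that: this is a conflict between text and tables, with a risk of omission. Weight also has no pre- or post-injection problem.
- **The T1 post-injection values are not lost.** SAP 8.2.1.2 tabulates raw data by visit and the SAP lists all collected data. This stands in part. Raw summaries would show the T1 shift in means. They would not give the spread of paired changes, nor a comparison in the same subjects once some have left. The gap is the missing reference for a change column.
- **Blood pressure is controlled.** Protocol 7.9 requires at least 5 minutes seated. So on-treatment blood pressure should not be called unrested; only its timing relative to the injection differs.
- **A single pre-dose baseline is defensible.** Post-injection readings suit a protocol that watches for acute reactions, and a baseline taken after the first dose builds the first response into the reference. This stands, and is why the pre-dose baseline should stay.
- **Timing is the same in all dose groups.** An acute effect common to the groups cancels in comparisons between them. This stands. A reader might infer that larger injection volumes at higher doses would produce a false dose-related trend, or might attach a value in mmHg to the artefact. Neither is supported. Nothing in the documents links volume to blood pressure or heart rate, Protocol 6.4 allows a different number and volume of injections within each dose, and any value would be pure assumption.

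The mismatch is also limited to clinic visits, since vital signs are taken only there and home or self-administration is allowed. The documents do not say whether a subject moving to Part 2 is dosed at the VF visit.

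**Conclusion.** Both points hold in limited form.

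For weight, the section text gives two post-screening time points and the tables give none, and the SAP specifies no change from baseline. How much data would be lost depends on how many sites work from the tables, which the documents cannot show. This is the more urgent half, because a missed weight cannot be replaced.

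For vital signs, the planned within-group change combines sustained change with any acute effect of the injection. The size and direction of the acute effect are unknown, and it may be nil. No effect size and no dose-related artefact should be claimed. Because every summary is descriptive, no test or decision rule depends on it; what is at stake is how a listed primary safety outcome is read. The conclusion assumes that sites follow Protocol 7.9 on timing and that no injection is given at VF and follow-up visits, where none is listed.

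**What to change.** 1. Add weight at T48 and VF to Protocol Tables 4-1 and 4-2 and to SAP Tables 2-1 and 2-2, to match Protocol 7.9. BMI follows by derivation. For T48 and VF visits already held, count how many have a recorded weight.
2. In SAP 8.2.4.10, specify change from baseline in weight by treatment group, with the screening value as baseline.
3. In SAP 8.2.1.2 (Vital Signs), keep the pre-dose baseline and add a summary of on-treatment change from the T1 post-injection reading. Report the T1 pre-to-post change separately. Compare VF and follow-up readings with the T1 pre-injection value, and state how a VF reading is classed if an injection was given at that visit.
4. Reconcile Table 4-1 footnote 6 with Protocol 7.9 on T2.

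**Cost.** One schedule row that 7.9 already requires, some SAP wording and a few more descriptive tables. No new procedure is needed. The added change from T1 post-injection has its own limit: it removes the acute response only as it was at the first injection. It should therefore stand beside the pre-dose change and not replace it.
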